1. TITLE

Examination of the Effectiveness and Implementation of Asthma Link™: A Real World Application of Supervised Asthma Therapy

2. EXTERNAL IRB REVIEW HISTORY*

N/A

3. PRIOR APPROVALS:

N/A

4. OBJECTIVES*

The objective of this pilot study is to evaluate the feasibility of an implementation study of Asthma Link as an effective method of evidenced-based practice of school-supervised asthma therapy in a real-world setting. If Asthma Link is found to be an acceptable practice with appropriate adoption and sustainability, it can serve as a scalable public health model for improving asthma medication adherence and combating the significant morbidity associated with pediatric asthma in the real world, rather than just research settings.

Aim 1: We will analyze process outcomes (acceptability, adoption, costs, sustainability) of Asthma Link™ in two pediatric practices.

Aim 2: Evaluate feasibility of a cluster RCT of Asthma Link™. The *primary trial outcomes* will be participant recruitment, retention, and intervention fidelity. The *secondary trial outcomes* will be differences in the frequency of asthma symptoms, emergency department visits, hospital admissions, courses of oral corticosteroids, spirometry values and school absences between Asthma Link™ and Enhanced Usual Care sites.

As each stage of Asthma Link™ evaluation builds upon the previous stage, we will submit separate IRB amendments and proposals for each stage of this project. The data collected from the proposed study will inform a large-scale cluster RCT to test the effectiveness and implementation of Asthma Link™.

5. BACKGROUND*

Countless pediatric asthma interventions have been successful in improving asthma outcomes in research settings, yet few are adopted into clinical practice to produce noticeable public health impact. Despite aggressive efforts to address remediable causes, childhood asthma still affects 12-15% of children in the urban United States, causes over 14 million missed school days annually and costs billions of dollars in healthcare expenditures.¹⁻³ Most of childhood asthma morbidity is attributable to non-adherence to a daily preventive medication, an inhaled corticosteroid (ICS).⁴⁻⁷ The highest asthma morbidity and the lowest ICS medication adherence rates occur in low income and minority children.⁸⁻¹⁰ These populations fall through the cracks as a result of failure to supervise and support adherence to preventive ICS medication. Recognizing this, the National Asthma Education and Prevention Program and the American Academy of Asthma, Allergy, and Immunology have urged that providers and researchers develop more effective adherence programs.^{11,12}

INVESTIGATOR STUDY PLAN

School-supervised administration of asthma therapy has helped improve medication adherence and improves asthma symptoms among children enrolled in research studies. There have been multiple studies that have shown that school-supervised asthma therapy not only improves medication adherence in children with asthma but also that this practice is safe, with no adverse effects seen.¹³⁻¹⁵ School-supervised asthma therapy has been established as safe and efficacious, and therefore asthma experts (including the American Academy of Pediatrics, American Academy of Allergy Asthma and Immunology, and the National Association of School Nurses) endorse school-supervised asthma therapy as the evidenced-based standard of care.¹⁶

However, despite the compelling evidence from studies and endorsement from experts, these tested school-supervised asthma interventions have not been widely adopted in practice. This is likely due to reliance on research staff for implementation and operations that are costly and highly resource intense, making them infeasible to adopt and sustain in the real world after research funding ends.

In response to this critical public health issue, we propose to study Asthma Link, which is a low-cost, low-intensity community-clinical based model of supervised asthma therapy in schools. Asthma Link is an established, ongoing clinical program that promotes the adoption of the evidenced-based practice of school-supervised asthma therapy in real world settings.

Asthma Link connects the three groups that play vital roles in the health of school-aged children with asthma: pediatric practices, school nurses, and families. Pediatricians identify and enroll children with poorly controlled asthma and medication non-adherence as part of their routine practice. They send the school nurse an order for daily, supervised inhaled steroid administration at school. Families bring the prescribed inhaler to school. The school nurse supervises the child's inhaler administration and provides adherence education, as part of her daily routine, to ensure adherence and proper inhaler/spacer technique. Ongoing communication occurs between the pediatric practice, the school nurse and families throughout the school year. Asthma Link is based on prior research studies that demonstrate the safety and efficacy of school-supervised asthma therapy. The goal of Asthma Link is for school-supervised asthma therapy to operate in a real-world setting, delivered by pediatricians, school nurses and families within their current routines and relying on minimal resources and no research staff.

The goal of the proposed study is to examine the effectiveness and implementation of Asthma LinkTM in sustainable real-world practice.

Preliminary Data:

The current proposed study builds from our prior research, which has informed the proposed study. To initially test Asthma LinkTM, we performed a small pre/post study (SEE IRB DOCKET # H00010546_2) of 84 children enrolled in Asthma LinkTM (mean age 10 years, 95% Medicaid insurance, 67% Latino, 19% Black). We observed that children enrolled in Asthma LinkTM experienced a 54% decline in emergency room visits, a 95% decline in hospital admissions and a 46% decline in rescue medication use over a one-year follow-up period ($p<0.001$),¹⁷ demonstrating that Asthma LinkTM merits further rigorous evaluation. Additionally, in order to examine the barriers and facilitators to Asthma LinkTM real-world implementation, (SEE IRB DOCKET # H00012920_1), we are interviewing program stakeholders which include school

INVESTIGATOR STUDY PLAN

nurses, parent-child dyads, and medical providers who were participating in the program in addition to public health and insurance officials. Specifically, in our interviews with 12 school nurses, we found that they perceive Asthma Link™ to be an acceptable program given the brief (<5min) time required and ease of incorporation into their existing routine.

Despite our promising results, Asthma Link™ needs to be tested against a comparison group, using a cluster randomized controlled trial (RCT). The first step is to perform a pilot cluster RCT to assess feasibility outcomes and health outcomes (Aim 2). Additionally, it is imperative to assess process outcomes (acceptability, adoption, costs, sustainability) of Asthma Link™ in new pediatric practices to ensure that school-supervised asthma therapy can be successfully scaled up and utilized in real world practice (Aim 1). We propose to test Asthma Link™ using a pilot cluster RCT of 4 pediatric primary care sites in Massachusetts.

6. INCLUSION AND EXCLUSION CRITERIA*

Child eligibility criteria for enrollment in Asthma Link™ (established clinical program):

- (1) children aged 6-17 years (enrolled in grade 1-12)
- (2) prescribed daily inhaled corticosteroid (ICS) for asthma;
- (3) 1 or more courses of oral steroids in the past 2 years OR 1 or more hospitalizations or ED visits for asthma in the past 2 years OR Asthma Control Test (ACT) score <19 OR 1 or more sick or urgent care visits for asthma (including telehealth) in the last year
- (4) parent/child report of poor ICS adherence on adherence checklist- i.e. child or parent says “Yes” when provider asks if they have difficulty remembering to take their medication or if they regularly take medication holidays or breaks;
- (5) able and willing to assent;
- (6) parental permission
- (7) English or Spanish speaking.

STUDY INCLUSION/EXCLUSION Criteria:

Child Inclusion criteria:

- 1) Meet the eligibility criteria for Asthma Link (as described above) with exception to (7)
- 2) Enrolled in Asthma Link™ (if randomized to the Asthma Link™ Condition)
- 3) Able and willing to provide informed assent
- 4) Must be English or Spanish speaking

Child Exclusion criteria:

- (1) Unable or unwilling to provide informed assent
- (2) Diagnosis of a serious co-morbid illness during the past 5 years
- (3) Developmental delay that would prevent study participation.
- (4) Planning on moving from primary residence or moving outside of the school district in the next 1 year
- (5) A sibling to a child participating in this study

Parent Inclusion criteria are:

- 1) Parent/guardian to patient
- 2) 18 years or older
- 3) Able to understand and communicate in English or Spanish

INVESTIGATOR STUDY PLAN

- 4) Able and willing to provide informed consent.
- 5) May or may not be or become pregnant

Medical Provider Inclusion criteria are:

- 1) Able and willing to provide informed consent

Medical Provider Exclusion criteria are:

- 1) Unable or unwilling to provide informed consent

School Nurse Inclusion criteria are:

- 1) Able and willing to provide informed consent

School Nurse Exclusion criteria are:

- 1) Unable or unwilling to provide informed consent

Asthma Champion Inclusion criteria are:

- 1) Able and willing to provide informed consent

Asthma Champion Exclusion criteria are:

- 1) Unable or unwilling to provide informed consent

Adults lacking capacity and prisoners are also excluded

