11. PROCEDURES INVOLVED*

Randomization. Two groups of two practices (4 practices in total) will be matched based on comparable size and percent of minority patients. Within each pair, practices will be randomly allocated to Asthma Link or the comparison condition, using a computerized function. This will result in two practices randomized to the Asthma Link condition and two practices randomized to the Enhanced Usual Care comparison condition.

Recruitment will be performed from each practice site until the target n=72 parent-child dyads (18 per site) are recruited. (see section 13 on “Sample size calculation”) Recruitment will begin during the 2021-2022 academic school year.

Procedure Steps:

1. Research coordinator (RC) identifies potentially eligible patients (children aged 6-17 years (enrolled in grade 1-12) years and prescribed a daily inhaled corticosteroid per medical record from most recent visit scheduled for a clinic visit) through the practice's office scheduling and medical record system (e.g., Epic). RC will also collect that patient's name, DOB, mailing and email addresses, phone number, insurance type (as a proxy for socioeconomic status), list of

INVESTIGATOR STUDY PLAN

medications, number of emergency room visits, number of hospital admissions and number of oral steroid courses for asthma relief.

2. RC creates a Lilac Form for any potentially eligible patients as described above. (Lilac form is an indicator to the medical provider seeing the patient that this patient is potentially eligible for study.)

3. Asthma Link condition: As part of clinical practice, medical provider will determine if patient is struggling with taking daily asthma medicine. If YES, then will introduce Asthma Link by saying “There is a clinical program that allows for your child to receive their daily asthma medicine at school supervised by the school nurse.” Child can be enrolled in Asthma Link per the usual clinical steps (see Asthma Link steps).

- After they are enrolled in Asthma Link, medical provider will give family one-page description of study (see Flyer) and state “Researchers at UMass are performing a study of children who are participating in Asthma Link, would you be interested in hearing more?”

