3a. Enhanced Usual Care comparison condition: Medical provider will determine if patient is struggling with taking daily asthma medicine, if YES, the provider will give family a one-page description of study (see Flyer) and state “Researchers at UMass are performing a study of children with asthma to learn about how to support them in taking their every day asthma medicine, would you be interested in hearing more?”

- Attached to the “Flyer” will be the Authorization to Contact form. (see Authorization to Contact form)
- If the parent agrees, the Lilac form with the family’s information is faxed to the Research Coordinator. The pediatric office will fax this form with a confidential cover form.
- The fact sheet will be mailed to the parent with a letter saying that the Research Coordinator will call or text them (see Fact Sheet).
- The Research Coordinator will only call the parent five times. The first and third time a message will not be left, but a text message will be sent stating “This is X from Asthma Link, can I call you at TIME?” The second, fourth, and fifth time a message will be left saying “This is X from the University of Massachusetts Medical School. I am calling about the material on Asthma Link I sent you. Please call me back at X.”
- A phone screen will be conducted to ensure study inclusion criteria (see phone script).
- The Research Coordinator will obtain informed consent from eligible participants, including parental permission for their child to participate, child assent to participate, and parental consent to participate. (see sections 30, 31 on Consent)
- After all questions are answered regarding the study by the parent, the Research Coordinator will send the baseline survey via email to the participant to be completed by the parent and child together or will complete the survey over the phone with the child and parent.
- The Research Coordinator will then access the child’s medical record and obtain the discharge summaries, the emergency service records, the office/clinic notes, the problem list, the pulmonary studies, the child’s list of medications, and the child’s height and weight (to help interpret the spirometry data).
- The Research Coordinator will then call the child’s pharmacy to obtain refill history for their daily ICS inhaler.

INVESTIGATOR STUDY PLAN

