- Risk of Spirometry: Spirometry is a routine, non-invasive clinical test that is commonly performed in children with asthma. This test has been used both clinically and in research without any adverse events.^{23,24} There are no risks associated with spirometry except for the potential for a slight dizzy feeling and/or temporary cough. These symptoms are not always present and are temporary. In order to minimize risks, the participant will be in a seated position with adult supervision and a trained technician will perform spirometry, with physician available by phone for concerns or questions. We will follow institutional policies for prevention of Covid transmission, which includes the technician wearing a surgical mask with eye protection and using a new disposable mouthpiece for each participant. For this study the test is performed without the intent of yielding direct health benefit.
- Risk of discomfort while answering questions: Some subjects may feel uncomfortable answering certain survey questions (e.g., questions about family income) however subjects will be notified that they are welcome to skip questions or withdraw from the study at any time without penalty.

Given that this is a minimal risk study, the only foreseeable risks to the subjects include the possible loss of confidentiality. To address this, all participants will be given information on ways to contact [name] and the University of Massachusetts Medical School IRB

Data and Safety Monitoring Board (DSMB)

Given that this is a minimal risk study (wherein participants agree to enroll in the study after they become part of the Asthma Link program if they are in the Asthma Link practices or after they fit study inclusion criteria if in the Enhanced Usual Care practices), participants will primarily be evaluated through surveys, interviews, and spirometry, and therefore a data monitoring committee and/or a data safety monitoring board is not appropriate for this study. Alternatively, the PI will periodically examine the data and should any research-related unexpected events arise, the PI will evaluate the event per the procedure listed above and will adhere to the institution's prompt reporting requirements. We do not anticipate any adverse events from this study as the primary procedures involve minimal risk surveys, checklists and routine clinical spirometry.

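### Only Asthma Link families must accept the programme before study entry, so the exploratory health contrast compares programme acceptors with eligible consenters, and the analysis section does not say so

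*Combined protocol and SAP*

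**What the plan says.** **Allocation.** Section 11 allocates four practices, in two matched pairs, and then recruits dyads from each practice. The provider scripts differ by arm, so allocation is known when families are approached.

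**Asthma Link entry.** Child inclusion criterion 2 in Section 6 reads "Enrolled in Asthma Link™ (if randomized to the Asthma Link™ Condition"). Section 11, step 3, gives the order: "After they are enrolled in Asthma Link, medical provider will give family one-page description of study". The script then describes researchers "performing a study of children who are participating in Asthma Link". Section 14 confirms that "participants agree to enroll in the study after they become part of the Asthma Link program if they are in the Asthma Link practices".

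**Enhanced Usual Care entry.** In Section 11, step 3a, the provider asks whether the child struggles with daily medicine and, "if YES, the provider will give family a one-page description of study". The script describes "performing a study of children with asthma to learn about how to support them". There is no programme to accept. Section 14 says that these families join once they meet the study criteria.

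**Recruitment prompts.** Section 24 places programme flyers in exam rooms at intervention sites and allows triage nurses there to prompt providers. It describes nothing similar for comparison sites.

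**Analysis.** Section 4 lists the health differences as secondary trial outcomes, ending with "spirometry values and school absences between Asthma Link™ and Enhanced Usual Care sites". Section 13 compares the arms by a t-test (parametric or not) or Poisson regression, plans intent-to-treat and completer analyses, and names no adjustment. It calls the health outcomes exploratory and includes effect size among the estimates to be used, with published data, in sizing a larger trial.

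**Counts.** Section 10 records families screened, eligible and refusing, with reasons, and a practice checklist of the percentage of eligible children enrolled.

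**The concern.** Randomising practices balances the eligible families in the two arms, in expectation. It does not balance families selected by a rule that depends on the arm. Accepting the programme means agreeing to school-supervised dosing and bringing an inhaler to school. Families who agree may differ from those who do not in organisation, motivation or severity, and these could affect symptoms, emergency visits and absences.

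A family that would decline the programme cannot enter the study at an Asthma Link practice, while a similar family can enter at a comparison practice. A reader who sees an intent-to-treat label would take the contrast as programme against enhanced usual care in the same kind of family. The entry rules do not ensure that.

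Recruitment, a primary feasibility outcome, is also touched. If programme decliners are not counted as refusals, recruitment rates by arm rest on different denominators.

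**Working it through.** **1. Entry steps side by side**

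| Step | Asthma Link | Enhanced Usual Care |
|---|---|---|
| Record screen and Lilac form | yes | yes |
| Provider asks about difficulty with daily medicine | yes | yes |
| Exam-room programme flyer, possible triage prompt | yes | not described |
| Family accepts the programme | required | no such step |
| Study offered, consent and assent | after acceptance | after the adherence question |

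The shared steps, including assent and parental permission, do not amount to accepting school supervision. An intent-to-treat analysis keeps entrants in their allocated arm; it cannot restore families who were never entrants.

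**2. Recruitment denominators**

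Let p be programme acceptance among eligible families, c the study consent rate among acceptors in either arm, and r the consent rate of decliners relative to acceptors.

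- Entrants per eligible family: p × c in Asthma Link, and c × [p + (1 − p)r] in the comparison arm.
- With r = 1 and p = 0.5: 0.5c against c. With r = 1 and p = 0.8: 0.8c against c.
- Entrants per family offered the study, with r = 1: c in both arms.

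The same data can thus show equal recruitment or a twofold difference, depending on whether programme decliners are counted.

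**3. Possible bias in the health contrast (illustration)**

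The documents give no acceptance rate, no acceptor-decliner difference and no consent rate among decliners. Assumed: p = 0.5 to 0.8; r = 1, 0.5 or 0.25; gap in outcome (apart from any programme effect) of 0.3 to 0.5 SD. Acceptors are assumed to consent at the same rate in both arms.

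Share of would-be decliners among comparison entrants: f = (1 − p)r / [p + (1 − p)r]. Absolute bias = f × gap, sign unknown.

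| p | r | f | Bias at gap 0.3 | Bias at gap 0.5 |
|---|---|---|---|---|
| 0.5 | 1 | 0.500 | 0.150 | 0.250 |
| 0.5 | 0.5 | 0.333 | 0.100 | 0.167 |
| 0.5 | 0.25 | 0.200 | 0.060 | 0.100 |
| 0.8 | 1 | 0.200 | 0.060 | 0.100 |
| 0.8 | 0.5 | 0.111 | 0.033 | 0.056 |
| 0.8 | 0.25 | 0.059 | 0.018 | 0.029 |

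**4. Comparison with the pilot's precision**

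Section 13 gives 36 dyads per condition, 18 per practice, and mentions ICCs of 0.01 and 0.05. They are applied here to a continuous health outcome. SE = sqrt(2/36 × DE), with DE = 1 + 17 × ICC.

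- No clustering: DE = 1, SE = 0.236 SD.
- ICC 0.01: DE = 1.17, SE = 0.255 SD.
- ICC 0.05: DE = 1.85, SE = 0.321 SD.

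The largest bias, 0.25 SD, is about one standard error (0.25/0.236 = 1.06; 0.25/0.321 = 0.78). The smallest, 0.018 SD, is negligible beside any of them. SD units do not carry over directly to count outcomes such as emergency visits.

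**The case against.** The strongest reply is that little hangs on this contrast. The health outcomes are secondary and exploratory. Section 13 itself says that pilots give no meaningful between-condition effect sizes and that the results will be combined with outside evidence. With two practices per arm, arm and practice are hard to separate in any case. The entry rule is openly stated in Sections 6, 11 and 14, and requiring programme enrolment suits the implementation aim. Section 10 already collects refusals and the percentage of eligible children enrolled. All of this stands, and it keeps the point minor. What remains is that Section 13 uses the intent-to-treat label without a caveat, still lists effect size as a planning input, and does not connect the Section 10 counts to the contrast. The checklist is not in the documents, so it may already separate the reasons for non-enrolment; the protocol does not say so.

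Two stronger readings are tempting. A reader might infer that the bias favours Asthma Link or is large enough to overturn a result. The documents give nothing from which to derive its sign or size. A reader might also infer that the Asthma Link baseline is contaminated by programme time, since study entry follows programme enrolment. No interval between the two is given, so this is not shown. Moreover, Section 11, step 1, has the coordinator collect "number of emergency room visits, number of hospital admissions and number of oral steroid courses for asthma relief" when screening records, before the programme is offered.

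**Conclusion.** The point holds, as a minor one. The entry asymmetry is explicit in the text and rests on no assumption. As planned, the health contrast compares programme acceptors with eligible consenters, recruited under different prompts; it is not an intent-to-treat estimate for eligible families. The bias of about 0.02-0.25 SD in either direction rests wholly on the assumed acceptance, gap and consent ratio. Within those ranges it is at most about one standard error, so the pilot could not reliably detect it. Retention and fidelity do not rest on the health contrast. Recruitment rates by arm do need the denominator made clear.

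**What to change.** **(a) Section 13, Statistical Analysis.** State that the health contrast compares programme acceptors with eligible consenters under differing recruitment prompts (Section 24); that it is not an intent-to-treat estimate for eligible families; and that the pilot effect size will not be used to size the larger trial without that caveat.

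**(b) Section 10, practice checklist.** Separate three outcomes for eligible children: not offered the programme, offered the programme and declined, and declined the study. The first two apply only at Asthma Link practices. Report the counts by practice and arm, with a table of baseline characteristics by arm.

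**Cost.** A short statement in Section 13, one or two extra checklist fields if the form lacks them, and a less favourable description of the secondary contrast. Recruitment, the intervention and the inclusion criteria are unchanged. Section 19 limits what practice staff may collect for research, so the new fields are best kept as counts and checked against that section.
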